1.3 Research Design and Methods

RR-MS patients will be recruited from the Robert Wood Johnson Center for MS under the direction of [name]. The patients will be asked to participate in the study during their regular clinical visit to the MS Center.

Inclusion criteria includes patients aged 21-65 Relapsing Remitting Multiple Sclerosis (RRMS) who met the 2017 McDonald criteria.

The first group (**Group A**) of MS patients (**n=25**) will receive a dietary fiber supplementation. They will consume 60 g/day of HFS for 12 weeks (High-fiber supplement group, Group-A). The supplement consists of a mixture of soluble fibers (from inulin and fibersol-2) and insoluble fibers (from oat bran, corn bran, wheat bran and sorghum bran) and it will be consumed as a drink.

The second group of MS patients (**Group B**) (**n=25**) will not consume any high fiber supplement.

The first group (**Group C**) of healthy volunteers (**n=25**) will receive a dietary fiber supplementation. They will consume 60 g/day of HFS for 12 weeks. Healthy volunteers will not have MS.

The second group (**Group D**) of healthy volunteers (**n=25**) will not consume any high fiber supplement.

For Groups A, B, C & D stool, and serum samples will be collected at 3 time points (baseline; Week 8; & Week 12).

Group E (n=25) will consist of 25 subjects with MS who experience an MS flare up.

These 25 subjects can be those participants with MS who are already part of the above study (Group A or B) and consent to 2 extra blood and 2 extra fecal samples collected at the time of the acute flare up and upon resolution of symptoms.

Screening visits will typically take place during routine MS follow up visit at the Robert Wood Johnson Center for MS. During this time, eligibility will be reviewed, and consent will be obtained once the patient has had time to review the study, have questions answered, and agree to participate. During this screening visit, details regarding the patients MS history, food allergies/intolerances, medical history, and medications will be recorded. Eligible participants will be asked to provide blood and stool samples for baseline assessment.

A. Research Procedures

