Multiple sclerosis is associated with gut dysbiosis. Notably, gut dysbiosis in MS is associated with the loss of bacterial taxa involved in fermentation of dietary fiber and the production of SCFA (3-5). Since SCFA can promote the differentiation of Foxp3Tregs, a decrease in SCFA-producing bacteria in gut microbiota would be a risk factor for MS. Recently, our collaborator, [name] at our institution, developed a HFS. His recent study suggests an association between intake of HFS and reduced gut dysbiosis and increased abundance of short chain fatty acid (SCFA)-producing gut bacteria in T2DM (1). Since increase in SCFA-producing bacteria may be beneficial for inflammatory diseases including MS, we will investigate whether HFS can promote the growth of SCFA-producing bacteria in MS patients and promote the development of regulatory immune cells.

The stool and serum will be collected at 3 time points (pre-HFS; 8 and 12 weeks after consumption of HFS) from MS patients. Similar samples will be obtained from the HFS treated and non-treated control group at similar time points. Fecal DNA will be extracted using the QIAamp PowerFecal DNA Kit (QIAGEN). DNA quality and quantity will be measured using the NanoDrop™ One microvolume UV-Vis Spectrophotometer (Thermofisher) and Qubit 1x dsDNA HS assay (ThermoFisher) respectively. Gut bacterial composition will be examined by 16S rRNA gene sequencing using the Ion GeneStudio S5 (Thermofisher) in [name] lab. QIIME 2 will be used to analyze the sequencing data to identify the amplicon sequence variants (ASVs). ASVs will then be grouped into guilds based on their abundance correlations. Biomarkers and microbiome-based prediction models will be explored at both the ASV and guild level using statistical methods such as Random Forest and Partial Least Squares regression models. Samples of potential significance will be shortlisted for subsequent whole genome metagenomic sequencing. Concentration of fecal and serum SCFAs will be measured by Rutgers metabolomics core facility. Since Vitamin-D (Vit-D) is one of the most important nutrients that affect immune modulation (6, 7), we will also measure serum Vit-D levels.

Next, we will assess the effect of HFS on intestinal permeability. MS is associated with gut dysbiosis and intestinal permeability (3-5, 8). Therefore, we will examine gut intestinal permeability (IP) by measuring the serum levels of zonulin, which is a biomarker of IP (9), using a zonulin ELISA kit

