We will also examine the development of inducible EAE in C57BL/6 mice transplanted with fecal samples. Germ-free C57BL/6 mice will be purchased from Taconic Inc. and expanded for the experiment. The fecal samples will be collected from regular diet- and HFS-treated HDs and MS patients as described above and transplanted into the germ-free C57BL/6 mice (10 in each group). The transplanted mice (7-9 week-old) will be immunized with MOG35-55 at 200 ug/mouse and injection with pertussis toxin at 100 ng/mouse. Development of EAE will be examined for 40 days. Demyelination and axonal loss in the brain and spinal cord will be examined by immunohistology

with anti-MBP and -Neurofilament Abs, respectively. Microbial composition, intestinal permeability, and development of Th-1, Th-17, Th-GMCSF and Foxp3 Tregs will be examined as described above.

3. Explore biomarkers of MS-associated gut dysbiosis and response to HFS:

RR-MS and healthy donors (21-55 year-old) from RWJ MS Centers will be asked to participate in this study according to institutional IRB guidelines. In this study, fecal and blood samples will be collected from RR-MS patients during relapse (before steroid treatment) and later during remission and examined for intestinal inflammation, permeability and microbial composition. We will enroll 25 patients based on sample size calculation using related previous studies with a statistical power of 80% (8, 20). The fecal samples (200 mg) will be dissolved in 0.5 ml PBS containing proteinase inhibitor and the supernatant will be collected. The concentration of intestinal inflammation biomarkers including Lcn-2, Calprotectin, and Lactoferrin, and a biomarker for intestinal permeability, serum zonulin, will be measured by ELISA assay. We will examine the association between increase in intestinal inflammation/permeability and disease activation.

The fecal samples collected from HFS-treated and un-treated MS patients at the 3 time points described in Aim-1, will be analyzed for intestinal inflammation and permeability as described above. We will simultaneously examine the microbial composition in the fecal samples as described in Aim-1 to determine if an association between MS relapse and gut dysbiosis exists.

C. Study Duration

Subjects participation will be 12-week period.

Study Timetable:

Upon IRB approval-Sept. 2023 Collection of blood and fecal specimens

Sept. 2021-Sept. 2023 Analysis of blood and fecal specimens

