Sept. 2021-Aug. 2023 Fecal transplantation in germ free mice and analysis for EAE

D. Endpoints

The primary endpoint will be detection of effect of HFS on intestinal microbial composition, intestinal permeability, production of SCFA, intestinal permeability, and immune cells in 25 MS patients between before and after intake of high-fiber supplement.

The secondary endpoint will be detection of biomarkers for intestinal inflammation-associated disease exacerbation in 25 MS patients.

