1.4 Preliminary Data

A. A high-fiber supplement selectively promotes a group of SCFA producing bacteria.

Recently, our collaborator, [name] at our institution, developed a high-fiber supplement (HFS). His study suggests an association between intake of HFS and reduced gut dysbiosis and

increased abundance of short chain fatty acid (SCFA)-producing gut bacteria, and demonstrated that HFS can ameliorate type-2 diabetes mellitus (T2DM) (1). This beneficial effect was associated with increased levels of SCFA, butyric acid (Fig.1B). Furthermore, HFS promoted the growth of 15 SCFAs-producing bacteria which mostly peaked at day 28 and remained stable afterward till the end of the trial (Day 84), while only 3 acetate producers among the 15 SCFA-producing bacteria were promoted in controls (Fig.1C). To test whether HFS-promoted microbiota can contribute to glucose homeostasis, fecal samples isolated from HFS-treated (W group) and non-treated (U group) T2DM patients were transplanted into germ-free mice and glucose homeostasis was examined in the transplanted mice. As shown in Fig.2, the transplanted microbiota from HFS-treated group improved glucose homeostasis. Since increase in SCFAs-producing bacteria may be beneficial for inflammatory diseases including MS, we will investigate whether HFS can promote the growth of SCFAs-producing bacteria in MS patients and promote the development of regulatory immune cells.

[figure not shown]

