1.5 Sample Size Justification

Our collaborator, [name] employed n = 27 in the HFS-treated group and n=16 in non-treated group and observed a significant effect of HFS on SCFA production in type 2 diabetes mellitus (T2DM) study (1). Since the therapeutic effect of HFS may be different between MS and T2DM, we sought the assistance of [name] who is a Biostatistician at Rutgers University. We selected the published MS studies that showed the effect of high vegetable diet on development of Tregs (n=10 in each group in this study) (12), and calculated a reasonable sample size using mean and standard deviation of the data, assuming a mean difference of 5% type I error and 80% power. Our sample size calculation indicated that n=20 in each group is sufficient to observe the statistical difference in the development of regulatory cells. Although there is no published data on the effect of diet on intestinal permeability in MS, a study of intestinal permeability in MS (n=14) vs healthy donor (HD) (n=16) showed statistically significant increase in intestinal permeability in MS patients compared to HD (8). Our sample size calculation also indicated that n=20 in each group is sufficient to observe a statistical difference. Based on our previous HFS-data and sample size calculation, we propose to enrol 25 patients in each group in Aim-1. Regarding the sample size in Aim-3, there is no published intestinal inflammation biomarker data in MS. Therefore, we used the data from an IBD study (20) where n=20 was sufficient to detect

differences in Lcn-2, lactoferrin, and zonulin between IBD vs HD. From our sample size calculation we propose to enroll 25 patients in each group in Aim-3.

Summary:

Stool, and blood samples isolated from 50 MS patients and 50 healthy controls will be used for gut permeability, bacteria DNA sequencing, immunology experiments, and MS animal experiments.

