1.6 Study Variables

A. Independent Variables, Interventions, or Predictor Variables

Experiment 1: Four groups (HDs and MS patients with and without HFS treatment).

Experiment 2: Four groups (Fecal samples from HDs and MS patients with & without HFS treatment).

Experiment 3: Two groups (MS patients with MS relapse and healthy volunteers).

B. Dependent Variables or Outcome Measures

Experiment-1: Percentage of pathogenic and non-pathogenic bacteria, intestinal permeability, and percentage of pathogenic and regulatory immune cells.

Experiment-2: Incidence and severity of EAE development.

Experiment-3: Intestinal inflammation and intestinal permeability.

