6.0 Data Management Plan

6.1 Data Analysis

6.2 Data Security

1. The study investigators will be utilizing Rutgers University REDCap (research electronic data capture). REDCap is a secure web application designed to support data capture for clinical studies.
2. Data will be stored in password protected computers and only authorized person involved in study will have access.
3. Data will be transferred via encrypted emails and password protected portable storage device.

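### The primary endpoint is worded as a before-after change in the 25 supplement-treated MS patients with no comparator, which disagrees with the plan's own four-group design

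*Combined protocol and SAP*

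**What the plan says.** Section 1.3 D gives one primary endpoint: the effect of the high-fiber supplement (HFS) on microbial composition, intestinal permeability, SCFA and "immune cells in 25 MS patients between before and after intake of high-fiber supplement". It names no comparator and no visit. That these 25 are Group A is an inference, but a safe one, because Group A (n=25) is the only MS group given HFS.

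Other sections describe a controlled study:

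- Section 1.3 has an untreated MS group (Group B, n=25) on the same sampling schedule: "For Groups A, B, C & D stool, and serum samples will be collected at 3 time points".
- Section 1.3 B, Experiment 3, plans to analyse both kinds of MS sample for inflammation and permeability: "The fecal samples collected from HFS-treated and un-treated MS patients at the 3 time points described in Aim-1".
- Section 1.5 reports that "n=20 in each group is sufficient to observe the statistical difference in the development of regulatory cells", and then sets enrolment at 25 per group.
- Section 1.6 A gives the independent variable: "Experiment 1: Four groups (HDs and MS patients with and without HFS treatment".

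None of these names an estimator or a deciding visit. The supplied text does not say how participants are assigned to A or B.

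**The concern.** A before-after contrast in one treated group measures the supplement's effect plus everything else that changes over 12 weeks: regression to the mean, season, background diet, MS therapy and assay drift. Group B is the part of the design that could separate these, and the endpoint leaves it out. An analyst following section 1.3 D would run a paired test in Group A. An analyst following sections 1.5 and 1.6 would compare groups. The two can reach different answers from the same data.

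Section 1.2 says that success here would justify launching a clinical trial of the supplement, so that decision would rest on whichever contrast is used.

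**Working it through.** **The plan's own figure.** Section 1.5 gives 20 per group at 5% type I error and 80% power. It cannot be reproduced forwards, because neither the mean difference nor the SD is given. Solved backwards as a two-sided two-sample t-test (an assumption; sidedness and test are not stated), with noncentrality d·√(n/2) and 2n − 2 degrees of freedom:

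- n = 20 per group: d ≈ 0.91 SD.
- n = 25 per group: d ≈ 0.81 SD.

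A paired test in 25 patients reaches 80% power at 0.58 SD of the change score. The per-group size and the endpoint as worded therefore address different questions.

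**Inputs for the illustration.** From the documents: 25 per group, 5% type I error, 80% power, baseline and week 12. Assumed: two-sided testing, equal SDs, a paired t-test, correlation r = 0.3, 0.5 or 0.7 between baseline and week 12, and a drift in SD units unrelated to HFS.

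**Before-after test in Group A, no HFS effect.** The SD of the change is √(2(1−r)) = 1.183, 1.000, 0.775. The noncentrality is √25 × drift / √(2(1−r)), with 24 df. For a 0.3 SD drift this is 5 × 0.3/1.183 = 1.27, 5 × 0.3/1.000 = 1.50 and 5 × 0.3/0.775 = 1.94.

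| Drift (SD) | r = 0.3 | r = 0.5 | r = 0.7 |
|---|---|---|---|
| 0.1 | 7% | 8% | 10% |
| 0.2 | 13% | 16% | 24% |
| 0.3 | 23% | 30% | 46% |

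**A versus B by ANCOVA, no HFS effect.** The residual SD is √(1−r²) = 0.954, 0.866, 0.714. The noncentrality is √12.5 × (drift in A − drift in B) / √(1−r²), with 47 df.

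| Drift pattern | r = 0.3 | r = 0.5 | r = 0.7 |
|---|---|---|---|
| 0.3 SD in both groups | about 5% | about 5% | about 5% |
| 0.3 SD in A, 0.15 SD in B | 8% | 9% | 11% |
| 0.3 SD in A only | 19% | 22% | 31% |

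The control group removes shared drift only, which is why the method of assignment belongs to this point.

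**Sensitivity.** Effect detectable with 80% power, 25 complete per group:

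| Contrast | r = 0.3 | r = 0.5 | r = 0.7 |
|---|---|---|---|
| Before-after in A | 0.69 SD | 0.58 SD | 0.45 SD |
| ANCOVA, A versus B | 0.77 SD | 0.70 SD | 0.58 SD |

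The ratios of ANCOVA to before-after are about 1.12, 1.20 and 1.28. All three ANCOVA values lie below the 0.81 SD implied by an unadjusted comparison at 25 per group.

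**The case against.** The strongest reply is that sections 1.5 and 1.6 already imply a comparison between groups, so section 1.3 D is only loose wording. Much of this stands: those sections do point that way, and a reader should not infer that the plan lacks a controlled design. But a list of predictors and a per-group sample size are not an estimator, and the only explicit statement of the primary endpoint says something else.

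The illustration is also hypothetical. No document gives a drift; at 0.1 SD the inflation is modest, and if only Group A drifts the repaired analysis is inflated too. This stands, and it limits what the numbers can show.

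Three stronger readings are tempting and are not supported:

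- **That the plan itself calls Group B the control.** Section 1.3 B says "Similar samples will be obtained from the HFS treated and non-treated control group at similar time points". This follows a sentence about MS patients and covers both treated and untreated people, so it may mean the healthy donors, as the word control does in sections 1.5 and 4.1.
- **That no analysis was planned.** "6.1 Data Analysis" is a heading with no text in the supplied document, but this may be an extraction or redaction gap. The point does not need it.
- **That the preliminary data show drift in untreated people.** Section 1.4 reports, of the diabetes study, "while only 3 acetate producers among the 15 SCFA-producing bacteria were promoted in controls". Those controls followed a recommended diet. This shows that a comparison group can change, not that untreated MS patients will.

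**Conclusion.** The endpoint sentence in section 1.3 D is wrong as written. It conflicts with the sampling schedule, the sample size and the independent variable elsewhere in the plan, and that conflict rests on stated text. Followed literally, it cannot separate an effect of HFS from change over time.

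The size is conditional: at assumed drifts of 0.1 to 0.3 SD and correlations of 0.3 to 0.7, false positives run from 7% to 46% against a nominal 5%. The point about assignment rests on silence in the supplied text, so it is a request for a statement. A reader might infer that the groups are self-selected; the documents do not say so.

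**What to change.** 1. Reword section 1.3 D so that the HFS effect in MS is the difference between Groups A and B at one pre-named visit. Week 12, the end of planned intake, is a reasonable choice. For univariate outcomes (for example Treg percentage, zonulin, SCFA) use ANCOVA or a mixed model adjusted for each participant's own baseline value. For microbial composition, compare the change between groups. Report the within-A change as descriptive.
2. State how participants are assigned to A or B. If assignment is not random, declare the comparison non-randomised, adjust for baseline MS therapy as numbers allow (section 4.1 C admits patients on several therapies and patients who decline them), and interpret the result accordingly. Adjustment does not remove drift that differs between the groups.

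The cost is protocol wording; Group B's samples are already planned. Relative to the before-after test, the detectable effect rises by about 12%, 20% or 28%. Relative to the per-group sizing in section 1.5, read as a two-sided two-sample t-test, nothing is lost.

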1.4 Preliminary Data

A. A high-fiber supplement selectively promotes a group of SCFA producing bacteria.

Recently, our collaborator, [name] at our institution, developed a high-fiber supplement (HFS). His study suggests an association between intake of HFS and reduced gut dysbiosis and

increased abundance of short chain fatty acid (SCFA)-producing gut bacteria, and demonstrated that HFS can ameliorate type-2 diabetes mellitus (T2DM) (1). This beneficial effect was associated with increased levels of SCFA, butyric acid (Fig.1B). Furthermore, HFS promoted the growth of 15 SCFAs-producing bacteria which mostly peaked at day 28 and remained stable afterward till the end of the trial (Day 84), while only 3 acetate producers among the 15 SCFA-producing bacteria were promoted in controls (Fig.1C). To test whether HFS-promoted microbiota can contribute to glucose homeostasis, fecal samples isolated from HFS-treated (W group) and non-treated (U group) T2DM patients were transplanted into germ-free mice and glucose homeostasis was examined in the transplanted mice. As shown in Fig.2, the transplanted microbiota from HFS-treated group improved glucose homeostasis. Since increase in SCFAs-producing bacteria may be beneficial for inflammatory diseases including MS, we will investigate whether HFS can promote the growth of SCFAs-producing bacteria in MS patients and promote the development of regulatory immune cells.

[figure not shown]

Fig. 1. A high-fiber diet selectively promotes a group of SCFA producers as the major active producers. (A and B) Changes in fecal concentrations of acetic acid and butyric acid. SCFAs were measured using gas chromatography, and amounts are expressed as milligrams per gram of dry feces (\pm SE). (C) Time-course changes in the abundance of the active SCFA producers. The sizes and colors of the circles indicate the average abundance and the coefficient of variance (CV) of the abundance of the strains, respectively. W group: intervention group on high-fiber diet composed of whole grains, traditional Chinese medicinal foods, and prebiotics. U group: control group consuming diet recommended based on the 2013 Chinese Diabetes Society guidelines for T2DM. Two-way repeated-measures ANOVA with Tukey's post hoc test was used for intra- and intergroup comparisons. * $P < 0.05$, ** $P < 0.01$, and *** $P < 0.001$ for comparison with day 0; # $P < 0.05$ for comparison with the U group at the same time point. n = 27 patients in the W group and 16 patients in the U group.

[figure not shown]

Fig. 2. Transplantation of fiber-altered gut microbiota improves glucose tolerance in mice. Fecal samples isolated from HFS-treated (W group) and non-treated (U group) T2DM patients were transplanted into germ-free mice before (W-pre and U-pre) and 84 days after treatment (W-post and U-post). Body weight (A), fasting blood glucose (FBG) (B) and fasting insulin (C) were examined 4 weeks after transplantation. Mice receiving transplant: n = 5 for W-Pre, W-Post, U-Pre and n = 4 for U-Post. *P <0.05, **P <0.01 and ***P <0.001 using one way ANOVA with a Tukey's post-hoc test for intra- and inter-group comparisons.

B. Gut-dysbiosis promotes spontaneous EAE in 3A6/DR2a mice

To examine the effect of gut microbiota on CNS autoimmunity, we created transgenic (Tg) mice that express the MS-associated HLA-DR2a gene and TCR gene specific to MBP87-99/HLA-DR2a that had been isolated from a 3A6 T cell clone derived from an MS patient (21) (Fig.3). The 3A6TCR/HLA-DR2a Tg mice were further crossed with MHC class II-KO mice to replace endogenous MHC class II with HLA-DR2a (referred to as 3A6/DR2a Tg mice). Interestingly, the MBP-specific 3A6 TCR Tg T cells do, in fact, spontaneously differentiate into GM-CSF⁺ Th1 and Th17 cells, and 20–30% of the 3A6/DR2a Tg mice develop spontaneous EAE in our SPF animal facility (Table 2) (19). Microbial infection has been suggested to be a possible etiology for MS; therefore, we examined the effect of gut microbiota on the development of spontaneous EAE. As shown in Fig. 4A, antibiotic treatment abrogated the development of spontaneous EAE, suggesting that the microbiota plays an essential role in the development of CNS autoimmunity. Gut dysbiosis, which alters the gut bacterial composition, has been associated with MS (3-5). Since fecal IgM levels increase in response to pathogenic enteric bacteria that lead to gut dysbiosis (22, 23), we examined IgM levels in fecal samples isolated from EAE and non-EAE mice. We found that increases in fecal IgM levels were associated with decreases in Foxp3 and CBLB gene expression and a subsequent development of spontaneous EAE (Fig.4B.C, and D). We then examined the microbial composition of fecal samples by 16S RNA gene analysis and found a marked expansion of *B. vulgatus*, *B. acidifaciens*, and *B. xylanisolvans* in the gut, which was associated with dysbiosis and the development of spontaneous EAE (Fig4.E) (19). These data suggest that gut dysbiosis is highly associated with a reduction in peripheral tolerance and the subsequent development of CNS autoimmunity. We will use this MS animal model to investigate the effect of HFS on CNS-autoimmunity.

[figure not shown]

Fig.3. Schematic diagram showing the expression of MS-associated HLA-DR2a gene and TCR gene specific to MBP87-99/HLA-DR2a in Transgenic (Tg) mice.

Gender	Ascending EAE Score							Atypical EAE	Severity (Mean \pm SD)	Frequency	Onset Age (Week-old)
	1.0	1.5	2.0	2.5	3.0	3.5	4.0+				
Male	20	1	15	1	16	3	0	5	2.0 \pm 0.9	61/213 (28.6%)	7.3 \pm 2.3
Female	17	1	9	4	23	2	1	7	2.2 \pm 0.9	63/254 (24.8%)	8.2 \pm 3.1
Total	37	2	24	5	39	5	1	12	2.1 \pm 0.9	124/467 (26.5%)	7.8 \pm 2.7

Table-2. Development of spontaneous EAE in 3A6/DR2a Tg mice.

[figure not shown]

Fig. 4. Gut-dysbiosis promotes spontaneous EAE in 3A6/DR2a mice. (A) Antibiotic treatment effect on the development of spontaneous EAE. Breeding pairs of 3A6/DR2a Tg mice were treated with a cocktail of ampicillin (1 mg/ml), metronidazole (1 mg/ml), neomycin (1 mg/ml), and vancomycin (0.5 mg/ml), and their offspring were continuously treated with antibiotics. The development of EAE was examined until 20 weeks of age (**P<0.001). (B) Development of spontaneous EAE in fecal IgM-lo (Rederived), fecal IgM-m, and IgM-hi mice. IgM-lo and -hi mice were determined by average fecal IgM concentration during the period from 5 weeks to 10 weeks of age. IgM-lo mice: <2.0 ng/mg total fecal protein, IgM-hi mice: \geq 2.0 ng/mg total fecal protein. 3A6/DR2a Tg mice (n=214) were divided into fecal IgM-hi (n=58) and fecal IgM-lo (n=156) groups. Development of EAE was examined in fecal IgM-lo (Rederived), fecal IgM-m, and fecal IgM-hi mice. (**P<0.0001). (C) Down-regulation of E3 ubiquitin ligase genes in CD4+CD25- T cells is correlated with the up-regulation of the complement C3 gene in whole spleen cells. Expression of E3 ubiquitin ligase *Cbl-b* and complement C3 in CD4+CD25- T cells and whole spleen cells, respectively, were measured by qPCR. (D) Frequency of CD4+ Vβ5.1+ Foxp3+ T cells in the CD4+ Vβ5.1+ T cell compartment of 5 to 10-week-old mice is shown. Mean \pm SEM (n=3-4). (*P<0.05, **P<0.01). (E) Fecal IgM levels were examined by ELISA and fecal DNA was isolated from rederived, fecal IgM-lo (<2.0 ng/mg total protein) non-EAE, fecal IgM-hi (\geq 2.0 ng/mg total protein) non-EAE, and IgM-hi EAE 3A6/DR2a Tg mice. Enteric bacterial species were identified by Illumina 16S rRNA sequence analysis. n=5~7.

C. Fecal Lcn-2 is a biomarker of spontaneous EAE

We had identified a biomarker for EAE-associated gut dysbiosis. IgM is produced in response to expanded enteric bacteria in the gut (22, 23); therefore, we examined the correlation between gut dysbiosis and fecal IgM levels in 3A6/DR2a Tg mice. As shown in Fig.4B, increase in fecal IgM was associated with development of spontaneous EAE. Fecal Lcn-2 is a well-known biomarker for gut dysbiosis in IBD as described in the background (20, 24); therefore, we also examined the levels of fecal Lcn-2 in healthy and EAE 3A6/DR2a Tg mice. As we expected, there was a high association between fecal IgM and fecal Lcn-2 (Fig. 5A) and increase in Lcn-2 levels was associated with development of spontaneous EAE (Fig.5B). Interestingly, fecal IgM levels increased 1-2 weeks before onset of spontaneous EAE; while fecal Lcn-2 levels increased 3-4 weeks before disease onset (Fig. 5C), suggesting that fecal Lcn-2 is an earlier and more sensitive biomarker for CNS autoimmunity than fecal IgM. We also detected the increase in fecal Lcn-2

levels in C57BL/6 mice upon induction of EAE (Fig. 5D). These spontaneous and inducible EAE data suggest that fecal Lcn-2 may be a possible biomarker for CNS autoimmune diseases including MS. Therefore, we will investigate the effect of HFS on intestinal inflammation and association between intestinal inflammation and disease exacerbation in MS using intestinal biomarkers including Lcn-2.

[figure not shown]

Fig.5. Fecal Lcn-2 is a biomarker of spontaneous EAE. (A) Association between fecal IgM levels and lipocalin-2 production. Fecal samples were collected from healthy and EAE mice, and concentration of IgM and lipocalin-2 was measured by ELISA. (B) Association between fecal Lcn-2 levels and spontaneous EAE. (C) Fecal Lcn-2 is a more sensitive biomarker for spontaneous EAE. Fecal Lcn-2 levels before and after clinical EAE onset are shown. Mean \pm SEM (n = 10). (D) Increase in Lcn-2 upon EAE induction in C57BL/6 mice. EAE was induced in C57 BL/6 mice by Immunization with Mog35-55/CFA and injection with pertussis toxin. Fecal Lcn-2 levels were analyzed by ELISA.

